#### Treatment administration:

Documented infusions with other FVIII products or with a dose of 0 IU will be excluded. Infusions with a missing dose will be counted for number of infusions and exposure days but will be excluded from other treatment administration analyses.

## 4.2 Primary Endpoint Analysis

The proportion and 95% exact (Clopper-Pearson) CI of participants with favorable outcome on the risk score-selected prophylaxis regimen will be described. The proportion will be provided overall, as well as by assigned prophylaxis regimen and by subgroup of history of FVIII inhibitors.

### 4.2.1 Definition of Endpoint

Occurrence of favorable outcome is the primary endpoint which is assessed by ABR and frequency of prophylaxis Jivi administration (/month) evaluated from Visit 2 (baseline) through Visit 6 (Month 6, EOS/ early withdrawal) among participants in the mITT.

Favorable outcome is defined as no change of the score-assigned dosing regimen with one of the following intra-individual measures:

- improved ABR and decreased frequency of administration.
- improved ABR with similar frequency of administration.
- decreased frequency of administration and similar ABR.

Change of the score-assigned dosing regimen is addressed in [section 0](#) below.

Definition for improved/similar ABR:

$$ABR_{post} - ABR_{pre} = \begin{cases} \geq 1 & \text{worsening} \\ (-1, 1) & \text{similar} \\ \leq -1 & \text{improved} \end{cases}$$

Definition for decreased/similar frequency of administration (/month):

$$Infusions_{post} - Infusions_{pre} = \begin{cases} \geq 2 & \text{worsening} \\ (-2, 2) & \text{similar} \\ \leq -2 & \text{improved} \end{cases}$$

Therefore, a favorable outcome is achieved when either:

$$ABR_{post} - ABR_{pre} \leq -1 \text{ and } Infusion_{post} - Infusion_{pre} < 2$$

or:

$$ABR_{post} - ABR_{pre} < 1 \text{ and } Infusion_{post} - Infusion_{pre} \leq -2$$

### 4.2.2 Main Analytical Approach

The analysis of the primary endpoint will be performed on the mITT population.

The entire study intervention period will be analyzed regardless of the score assigned dosing regimen (i.e. during the first 8 weeks on the study).

The strategy for primary endpoint analysis, including how to deal with participants who switch regimen frequency is listed below:

- A switch to a higher frequency regimen than the one assigned by the score, due to a bleed during study, is considered as non-favorable outcome
- Participants who switch due to other reasons than bleeding events (e.g. personal decision, study compliance issues, or changes in physical activity level) will be censored at the time of regimen change
  - switch after 4 months ( $> 122$  days): participant data will be analyzed until censoring
  - switch prior to 4 months ( $\leq 122$  days): participant data will not be used for analysis, as it is assumed that a shorter duration will not be sufficient to correctly estimate the ABR and would bias the results.

Note: a decrease in regimen per score assignment (during the first 8 weeks) is not considered a switch as discussed above.

Favorable outcome assessed by total ABR and frequency of administration (/month) is evaluated after considering regimen switch events.

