#### **7.1.1 Inhibitor Development**

Any inhibitor development ( $\geq 0.6$  BU/mL, confirmed; see [Section 9.4.4.1](#)) is considered a SAE. Discontinuation of study intervention due to a high titer inhibitor development (titer  $> 5$  BU/mL) should be considered if the investigator believes that it is in the best interest of the participant and/or if bypassing agents are needed to treat bleeds. Participants who discontinue study intervention due to inhibitor development cannot continue in the study and will be withdrawn.

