#### Definitions

- No regimen change during study: participant is treated according to the score-assigned regimen and does not deviate or switch frequency.
- Improved ABR: Reduction from pre-study ABR is  $\geq 1$ .
- Similar ABR: Absolute change from pre-study ABR is  $< 1$ .

- Worse ABR: Increase from pre-study ABR is  $\geq 1$ .
- Decreased frequency of administration: Reduction from pre-study in number of infusions per month is  $\geq 2$ .
- Similar frequency of administration: Absolute change from pre-study in number of infusions per month  $< 2$ .
- Worse frequency of administration: Increase from pre-study in number of infusions per month is  $\geq 2$ .

Pre-study ABR and treatment frequency is based on data from a minimum of 6 continuous months (up to a maximum of 12 months) of stable SHL prophylaxis at any given time within the 12 months prior to screening. Stable SHL prophylaxis is defined as a minimum of 18 weeks of treatment in a 6 (consecutive) calendar month period in the 12 months prior to the screening visit.

A switch to a higher frequency regimen due to a bleed during study is considered as non-favorable outcome, whereas participants who switch due to other reasons (e.g. personal decision, study compliance issues, or changes in physical activity level) will be censored at time of switch.

The number (frequency) of participants switching the risk score-selected dosing regimen will be summarized.

As sensitivity analyses, the proportion of participants with favorable outcome on the risk score-selected prophylaxis regimen will be presented by inhibitor history.

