**Table 3: Analysis Sets**

Participant Analysis Set	Description
Enrolled	All participants who signed the ICF
Modified intention-to-treat (mITT) set	All enrolled participants who had received at least 1 dose of study intervention, who have infusions/bleeding data from the diary and CRF available, and who have been followed for a minimum of 4 months.
Safety analysis set	All participants who had received at least 1 dose of study intervention.

Abbreviations: CRF = case report form; ICF = informed consent form.

Final decisions regarding the assignment of participants to analysis sets will be made during the review of study data and documented in the final list of important deviations, validity findings and assignment to analysis set(s).

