#### **4.2.3 Sensitivity Analysis**

The following analysis will be performed if numbers of participants in the mITT population with and without history of FVIII inhibitors are each  $\geq 5$ : As sensitivity analyses, the proportion of participants with favorable outcome on the risk score-selected prophylaxis regimen will be presented by inhibitor history.

The following analysis will be performed if  $> 3$  participants in the safety analysis set are excluded from the mITT: The proportion of participants with favorable outcome will be reported for the safety analysis set, assigning non-favorable outcome to participants who discontinued or switched regimen prior to 4 months.

A further sensitivity will be conducted, assigning non-favorable outcome to all participants who discontinued or switched regimen at any time during study.

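### SAP 4.2.2 fails a bleed-driven step-up in frequency but has no rule for permanently stopping Jivi, so a late stop for treatment failure can still be scored favorable

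*SAP*

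**What the plan says.** SAP 4.2.2 sets out the primary analysis, "including how to deal with participants who switch regimen frequency is listed below". It has two branches. A step up in frequency, "due to a bleed during study, is considered as non-favorable outcome". A switch for any reason other than a bleed is censored. If that switch falls after 122 days, "participant data will be analyzed until censoring"; if earlier, the participant is left out. Permanent discontinuation appears in neither branch.

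SAP 4.2.1 has the endpoint "evaluated from Visit 2 (baseline) through Visit 6 (Month 6, EOS/ early withdrawal) among participants in the mITT". SAP Table 3 admits to the mITT set treated participants with diary and CRF data "who have been followed for a minimum of 4 months". SAP 4.1.1.1 and 4.1.1.4 compute ABR and frequency from Visit 2 to the Visit 6/EOS date.

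Protocol 9.4.2 defines no regimen change as: "participant is treated according to the score-assigned regimen and does not deviate or switch frequency". Stopping is not named there.

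The protocol foresees stops for treatment failure. Section 7.1.1 states: "Participants who discontinue study intervention due to inhibitor development cannot continue in the study and will be withdrawn". Section 8.3.1 provides for stopping Jivi when drug effect is lost. The endpoint rules mention neither case.

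SAP 4.2.3 plans a further sensitivity analysis, "assigning non-favorable outcome to all participants who discontinued or switched regimen at any time during study".

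**The concern.** The primary proportion is meant to show whether the score picked a suitable regimen. Moving up one interval because of a bleed is a partial failure of that choice, and it is always non-favorable. Abandoning Jivi for insufficient bleed control, an inhibitor or loss of efficacy is at least as serious, yet no sentence classifies it. If the programmer applies the SAP formulas as they stand, a late stop is judged only on ABR and frequency to that date and may pass. The ordering of the two events is then inverted. Compared with counting such stops as failures, the omission can only raise the headline proportion or leave it unchanged.

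**Working it through.** **1. The plan's own figures.** The exact Clopper-Pearson interval for 14/20 = 70% is 45.7% to 88.1%, width 42.4 points, as SAP Table 4 states. The frequency examples in SAP 4.1.1.4 also reproduce: 30.4375 × 52/182 = 8.6964 and 30.4375 × 32/182 = 5.3516 per month.

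**2. Is a late stopper analyzed?** The mITT set needs 4 months of follow-up, which is 4 × 30.4375 = 121.75 days. A participant who stops after that qualifies. The 122-day cut-off in SAP 4.2.2 itself concerns non-bleed switches; discontinuers come in through the mITT definition. I take EOS as the day of stopping, following Protocol 7.1, which ends participation with an EOS visit. Protocol 7 instead encourages continued follow-up. The two sections must be reconciled, but the point here does not depend on which one applies.

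**3. Does either branch of SAP 4.2.2 catch the stop?**
- A stop for bleeding is not a move to a higher frequency, and the censoring branch is limited to reasons other than bleeding. It fits neither branch.
- A stop for an inhibitor or loss of efficacy, if read as a switch for a non-bleed reason, is censored and its data are analyzed once past Day 122. It can still be favorable.

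**4. Example (assumed values).** Pre-study ABR 8 (+3), 3x/week (0), no target joint (-1), vWF from 100% to below 150% (0), sedentary (0). The total is 2, medium risk, so Q5D after 4 weeks. Two bleeds by Day 140.
- Pre-study frequency: 3 × 30.4375/7 = 13.04 per month.
- ABR: 365.25 × 2/140 = 5.22. Change 5.22 - 8 = -2.78, improved.
- Doses: 8 (Days 1-28) + 23 (every 5 days, Days 29-139) = 31. Frequency: 30.4375 × 31/140 = 6.74. Change 6.74 - 13.04 = -6.30, decreased.

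If Jivi is stopped that day, the SAP 4.2.1 formula gives favorable. If the participant steps up that day because of the bleed, SAP 4.2.2 gives non-favorable.

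**5. Possible, not automatic.** Take a stop at Day 130 on Q5D after 3x/week SHL: 29 doses, 30.4375 × 29/130 = 6.79 per month, change -6.25 (decreased). The ABR change must then be below +1. The largest number of bleeds that still passes is:

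| Pre-study ABR | 0 | 2 | 4 | 6 | 8 | 10 |
|---|---|---|---|---|---|---|
| Bleeds by Day 130 | 0 | 1 | 1 | 2 | 3 | 3 |

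A stop for an inhibitor or loss of efficacy with no bleeds has ABR 0, so it passes at any pre-study ABR. After 2x/week SHL the test is harder. Pre-study frequency is 2 × 30.4375/7 = 8.70, so the change on Q5D is 6.79 - 8.70 = -1.91. That is only similar, and ABR must also improve by at least 1.

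**6. Size.** The documents give no rate for such stops. Assuming 0 to 3 of 14 favorable participants out of 20 are late stops for these reasons, reclassifying them gives:

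| Reclassified | Proportion | 95% CI |
|---|---|---|
| 0 | 14/20 = 70% | 45.7 to 88.1 |
| 1 | 13/20 = 65% | 40.8 to 84.6 |
| 2 | 12/20 = 60% | 36.1 to 80.9 |
| 3 | 11/20 = 55% | 31.5 to 76.9 |

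Each case is 1/20 = 5 points, or 1/25 = 4 points at N=25.

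**The case against.** A reader might infer that the plan is simply wrong and knowingly scores treatment failures as successes. The documents do not support that. No sentence calls a stop favorable. The protocol definition requires treatment according to the assigned regimen without deviation, and the regimens have stated durations. Someone who stops at Day 140 is arguably no longer treated as assigned. The SAP also declares no change to the protocol's analyses, so that definition still stands. This part of the objection holds: the defect is a missing rule and an inconsistency. It does not settle the matter, because SAP 4.2.1 and 4.2.2 never apply the definition to stopping. The last analysis in SAP 4.2.3 would also have no reason to fail discontinuers if the main analysis already did so.

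That sensitivity analysis is unconditional, so the worst case will be reported, and SAP 4.6.1 tabulates discontinuation reasons. This stands as a bound. It does not isolate treatment failure, since neutral stops and switches fail with the rest. The safety-set sensitivity analysis concerns events before 4 months and does not reach this case.

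Rarity also stands. Protocol 2.3 reports no new or confirmed inhibitors in the clinical studies. Protocol 8.4.7 places the reported loss-of-efficacy events within the first 4 exposure days and in children under 6. For extended-interval participants, the response to repeated bleeds in Protocol 6.5 is a step-up, which already fails. A stop after many bleeds will usually fail on ABR anyway. The example in the working is therefore an illustration, not an expected case.

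Finally, whether an inhibitor shows that the score chose the wrong interval is debatable, so counting it as failure is partly a choice of endpoint definition. That is a reason to state the choice in advance.

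**Conclusion.** The point holds as a cheap improvement. Followed literally, the SAP can score a late stop for bleeding, inhibitor or loss of efficacy as favorable while it always fails a bleed-driven step-up. The protocol wording can be read the other way, so the primary endpoint is not fully defined for these participants. The size is 5 points per case at N=20 and 4 at N=25, always in the flattering direction relative to counting the stop as a failure. Few cases are expected, in a descriptive study whose interval at 14/20 is already 42.4 points wide. This rests on EOS falling at the day of stopping and on the SAP formulas being applied without an unwritten exclusion. It would be wrong to infer that every late stop becomes favorable, or that the headline will be materially inflated: the thresholds must still be met, and the documents give no rate.

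**What to change.** Add to SAP 4.2.2, consistent with Protocol 9.4.2: *Permanent discontinuation of Jivi for insufficient bleed control, confirmed inhibitor or loss of efficacy is classified as non-favorable in the primary analysis, whatever the ABR and frequency to that point.* Leave other discontinuations under the current rule, list the reason for each, and keep the SAP 4.2.3 sensitivity analysis unchanged. Membership of the mITT set does not change.

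The cost is one sentence before database lock, using the discontinuation reasons already tabulated under SAP 4.6.1. The documents do not show that insufficient bleed control is a listed category, so the team should confirm how it will be identified. The rule relies on an investigator-attributed reason in an open-label study, and the proportion may be slightly less favorable. This is an endpoint classification only and changes no clinical management.

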#### **4.2.3 Sensitivity Analysis**

The following analysis will be performed if numbers of participants in the mITT population with and without history of FVIII inhibitors are each  $\geq 5$ : As sensitivity analyses, the proportion of participants with favorable outcome on the risk score-selected prophylaxis regimen will be presented by inhibitor history.

The following analysis will be performed if  $> 3$  participants in the safety analysis set are excluded from the mITT: The proportion of participants with favorable outcome will be reported for the safety analysis set, assigning non-favorable outcome to participants who discontinued or switched regimen prior to 4 months.

A further sensitivity will be conducted, assigning non-favorable outcome to all participants who discontinued or switched regimen at any time during study.

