## 4. Statistical Analyses

### 4.1 General Considerations

Statistical analyses will be performed using SAS release 9.4 or higher (SAS Institute Inc., Cary, North Carolina, US).

All variables will be analyzed descriptively with appropriate statistical methods: categorical variables by frequency tables (absolute and relative frequencies) and metric (or continuous) variables by sample statistics (i.e. mean, standard deviation [SD], minimum, median, quartiles, and maximum). The number of data available and missing data will be calculated

for metric data. Continuous variables will be described by absolute value and as change from baseline per analysis time point, if applicable.

All data will be presented in the participant data listing as they are recorded on the electronic case report form (eCRF), eDiary and Interactive Voice/Web Response System (IxRS), i.e. partially missing data will appear as such.

The primary analysis will be performed after the database lock after Last Participant Last Visit.

The mITT set will be used to analyze endpoints related to the effectiveness objectives and the safety analysis set will be used to analyze the endpoints and assessments related to safety. Data will be pooled across study sites for all reporting of participant characteristics, primary, secondary, and safety endpoints.

Analysis will be presented overall for the combined risk score groups. Some tables will be stratified by the risk score-selected dosing regimen. Analysis of risk score-selected dosing regimen will include the entire treatment period. The first 8 weeks on study will not be presented separately. Safety listings will include assigned dosing regimen, based on risk score, and actual current dosing regimen at start of AE or time of assessment. Safety summaries will be presented only overall, for the combined risk score groups.

Subgroup analysis of study endpoints and safety events by history of FVIII inhibitors will be presented only if the mITT set includes at least 5 participants in each category, with and without history of FVIII inhibitors.

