#### **4.1.1 Data Rules**

##### **4.1.1.1 Annualized bleed rate (ABR)**

Pre-study ABR is reported in History of Hemophilia eCRF as 'ABR during period of stable SHL treatment'.

The ABR response is calculated over the entire intervention period:

- Intervention period (days) = (1 + Visit 6/EOS date – Visit 2 date)

The ABR is calculated using the number of bleed events reported to the eDiary. Types of bleed event and counting of bleeds are described in the section below.

The ABR for each type of bleed will be calculated as:

- $ABR = 365.25 \times \# \text{ of bleed events} / \text{Intervention period (days)}$ 
  - ABR will be rounded to 2 decimal places

Improved, similar, or worsening ABR will be assessed by comparison to pre-study ABR:

$$ABR_{post} - ABR_{pre} = \begin{cases} \geq 1 & worsening \\ (-1, 1) & similar \\ \leq -1 & improved \end{cases}$$

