**4.1.1.4 Frequency of Administration**

Baseline frequency of administration is reported in Previous Hemophilia Treatment for the past 6 months eCRF as ‘Previous Hemophilia Treatment during the stable SHL period’ and is converted to frequency per month.

The frequency of administration response is calculated over the entire intervention period:

- Intervention period (days) = (1 + Visit 6/EOS date – Visit 2 date)

The frequency of administration (/month) will be assessed using the record of prescribed dose regimen in the eCRF. These following are example calculations of the risk group planned dose frequency:

Example 1: Participant in high risk score group was prescribed 2x/week on Day 1 and remained in study until Day 182 (26 weeks) with no prescribed dose change. The total prescribed number of dose administrations is 26 weeks x 2/week. The frequency (/month) of prescribed Jivi prophylaxis is  $30.4375 \times$  total prescribed number of dose administrations/ dose interval (days) =  $[30.4375 \text{ (days/month)} \times 52] / 182 \text{ (days)} = 8.6964 \text{ / month}$ .

Example 2: Participant in low risk score group was prescribed 2x/week on Day 1, Q5D on Day 29, and Q7D on Day 57. The participant remained in study until Day 182 with no other prescribed dose change. The frequency of prescribed Jivi prophylaxis is  $30.4375 \text{ (days/month)} \times 32 \text{ total doses} / 182 \text{ (dose interval days)} = 5.3516 \text{ / month}$ .

- Frequency of administration (/month) =  $30.4375 \times$  total doses over intervention period of prescribed Jivi prophylaxis / Intervention period (days)
  - Frequency of administration will be rounded to 2 decimal digits.

Improved, similar, or worsening frequency of administration will be assessed by comparison of prescribed prophylaxis to the baseline frequency of administration (each expressed as infusions per month):

$$Infusions_{post} - Infusions_{pre} = \begin{cases} \geq 2 & \text{worsening} \\ (-2, 2) & \text{similar} \\ \leq -2 & \text{improved} \end{cases}$$

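### Treated participants who leave before 4 months fall out of the primary favorable proportion, and the one analysis explicitly set on all treated participants is skipped when only 1 to 3 are excluded

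*SAP*

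**What the plan says.** SAP 4.2.1 defines the primary endpoint as "evaluated from Visit 2 (baseline) through Visit 6 (Month 6, EOS/ early withdrawal) among participants in the mITT". SAP Table 3 limits the mITT to treated participants "who have infusions/bleeding data from the diary and CRF available, and who have been followed for a minimum of 4 months". SAP 4.1 sets the default: "The mITT set will be used to analyze endpoints related to the effectiveness objectives".

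SAP 4.2.3 then plans two analyses that count leavers and switchers as non-favorable:

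- **Safety-set analysis.** It runs only if more than 3 "participants in the safety analysis set are excluded from the mITT: The proportion of participants with favorable outcome will be reported" for the safety set. Those who discontinued or switched before 4 months count as non-favorable.
- **Further analysis.** It has no trigger and no named set: "A further sensitivity will be conducted, assigning non-favorable outcome to all participants who discontinued or switched regimen at any time during study".

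For participants who switch for reasons other than bleeding, SAP 4.2.2 discards the data if the switch comes by Day 122. After Day 122, "participant data will be analyzed until censoring". The data rules differ. In SAP 4.1.1.1, "The ABR response is calculated over the entire intervention period", and in SAP 4.1.1.4, "The frequency of administration response is calculated over the entire intervention period". Both define that period as 1 + Visit 6/EOS date − Visit 2 date.

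**The concern.** The endpoint asks whether the score chose a workable regimen. A participant whose treatment failed early is evidence on that question, yet is removed from the proportion. Protocol 7.1 says a participant who permanently stops study drug does not remain in the study, and Protocol 7.2 requires withdrawal for a neutralizing antibody. Protocol 8.4.7 reports that hypersensitivity and loss-of-efficacy events occurred within the first 4 exposure days. At twice-weekly dosing in 3- and 4-day intervals, the fourth exposure day is Day 11 or 12, so a participant withdrawn for such an event cannot reach 4 months.

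The direction of bias depends on who leaves. The primary figure is too high if leavers are failures, unaffected if they do as well as the rest, and too low if they do better. A proportion that counts all treated participants shows how far this matters, and at 1 to 3 exclusions it may never be reported.

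The period conflict is a second route to error: a programmer who follows the formulas literally would contradict the censoring rule.

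**Working it through.** **1. The plan's own figure.** The exact 95% limits are the 0.025 quantile of Beta(x, n−x+1) and the 0.975 quantile of Beta(x+1, n−x). For 14/20 this gives 45.7% to 88.1%, width 42.4, as in SAP Table 4. Ten rows of that table were recomputed and all agree.

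**2. What the trigger tolerates.** Taking 20 or 25 as the number treated (SAP 5 expects 20–25 enrolled), three exclusions are 3/20 = 15% or 3/25 = 12%.

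**3. Effect of k exclusions.** With x favorable among N treated, the primary result is x/(N−k) if the excluded are all failures and (x−k)/(N−k) if all would have been favorable. Both are compared with x/N.

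| N, all-treated result | k | excluded all failures | excluded all favorable |
|---|---|---|---|
| 20, 14/20 = 70.0% | 1 | 14/19 = 73.7% (+3.7) | 13/19 = 68.4% (−1.6) |
| | 2 | 14/18 = 77.8% (+7.8) | 12/18 = 66.7% (−3.3) |
| | 3 | 14/17 = 82.4% (+12.4) | 11/17 = 64.7% (−5.3) |
| 25, 17/25 = 68.0% | 1 | 17/24 = 70.8% (+2.8) | 16/24 = 66.7% (−1.3) |
| | 2 | 17/23 = 73.9% (+5.9) | 15/23 = 65.2% (−2.8) |
| | 3 | 17/22 = 77.3% (+9.3) | 14/22 = 63.6% (−4.4) |

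The exact interval for 14/17 is 56.6% to 96.2%. If nobody in the mITT switches or discontinues, the further analysis run on the mITT also reads 14/17, and 14/20 is not reported. Starting instead from an mITT result near 70%: 12/17 = 70.6% [44.0, 89.7] becomes 12/20 = 60.0% [36.1, 80.9]. Protocol 2.1 expects a favorable outcome in at least 70% of those enrolled, so the choice of denominator can move the estimate across that mark.

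**4. How often the gap opens.** The current plan gives no exclusion rate, so a range is assumed. The upper end is 10/70 = 14.3%, from the superseded plan of about 60 evaluable completers out of 70. It is only a rough upper guide, because evaluable is undefined there and the mITT needs only 4 months. The binomial chance of 1 to 3 exclusions (someone is left out and the trigger does not fire) is:

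| Assumed rate | N = 20 | N = 25 |
|---|---|---|
| 2% | 33% | 40% |
| 5% | 63% | 69% |
| 10% | 75% | 69% |
| 14.3% | 64% | 49% |

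**5. Period conflict.** Two assumed participants, both with score 5 (high risk, 2x/week), pre-study 2x/week = 2 × 30.4375/7 = 8.70 infusions/month, a non-bleed switch to Q5D on Day 127, and EOS on Day 182.

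- Scores from SAP Table 1 (bleeding rate, frequency, target joints, vWF, activity). Case A: +3 −1 +1 +2 +0 = 5. Case B: +2 −1 +1 +2 +1 = 5.
- Frequency to Day 126: 36 doses, 30.4375 × 36/126 = 8.70 (similar). To Day 182: 12 further Q5D doses, counted as in SAP Example 2, 30.4375 × 48/182 = 8.03, a change of −0.67 (similar).
- Case A, pre-study ABR 6.0, 2 bleeds by Day 126 and none after. To Day 126: 2 × 365.25/126 = 5.80, change −0.20, similar, so non-favorable. To Day 182: 2 × 365.25/182 = 4.01, change −1.99, improved, so the favorable categories are met.
- Case B, pre-study ABR 4.0, 1 bleed by Day 126 and 1 after. To Day 126: 365.25/126 = 2.90, change −1.10, improved, so favorable. To Day 182: 4.01, change +0.01, similar, so non-favorable.

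The classification reverses in both directions.

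**The case against.** The strongest reply is that the further analysis already closes the gap. It is unconditional, follows directly on the safety-set analysis, and refers to everyone who discontinued at any time, which naturally includes early leavers. On that reading the all-treated count is reported whatever the trigger does. This reading is possible. However, the sentence names no set, and SAP 4.1 and 4.2.1 both point to the mITT. On either reading it does count as non-favorable an early non-bleed switcher who stayed in follow-up for 4 months, so the gap is limited to treated participants outside the mITT.

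Second, little is hidden. SAP 4.6.1 tabulates analysis sets and discontinuation reasons, so a reader could often rebuild 14/20 from 14/17 and 20 treated. The study tests no hypothesis and concedes low precision. This stands, and it limits the severity. But with no test, the point estimate and its denominator are the main product.

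Third, the +12.4 points need exactly three exclusions, all failures. At N = 20 the chance of exactly three is 0.6%, 6%, 19% and 24% at the four assumed rates. At 2% and 5% a single exclusion makes up 82% and 60% of the tabled chance, with an effect of at most +3.7. At 14.3% the trigger itself fires 32% (N = 20) or 49% (N = 25) of the time. All of this is correct. Loss of efficacy is also described mainly in children under 6, so that exit route may be rare here.

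Fourth, the specific rule in SAP 4.2.2 could be read as overriding the general formulas. That is the sensible intent, and SAP 4.5.1 shows the censoring date is operational, since it separates dose until censoring from dose until EOS. The ABR and frequency formulas make no such distinction.

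**Conclusion.** The concern holds, as a should-fix point. Early leavers are outside the primary proportion, and the only analysis explicitly set on all treated participants is not required at 1 to 3 exclusions. Whether the further analysis fills the gap depends on a set the SAP does not name. For all-treated results near 70%, the primary figure could differ from the all-treated proportion by +2.8 to +12.4 points if the excluded are failures, or −1.3 to −5.3 if they would have been favorable. These shifts lie inside an interval about 40 points wide. The exclusion rates are assumed and the sign depends on who leaves. The period conflict is real as written, but it affects only non-bleed switchers after Day 122; the two cases are constructed to show that the classification can go either way.

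**What to change.** Keep the primary mITT analysis and the censoring rule, and make four changes.

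1. In SAP 4.2.3, delete the condition of more than 3 exclusions and always report the safety-set proportion beside the primary result.
2. State that the further sensitivity analysis uses the safety analysis set, and that treated participants excluded only for missing diary or CRF data also count as non-favorable. Call only this version a conservative bound, because in item 1 non-bleed switchers after Day 122 can still be favorable.
3. In SAP 4.1.1.1 and 4.1.1.4, state that for participants censored under 4.2.2 the period ends at the censoring date for bleeds, doses and days. Align the Visit 6 wording in 4.2.1.
4. Reconcile Protocol 7, which encourages participants who stop treatment to stay in follow-up, with Protocol 7.1, which says they do not remain in the study. This decides who reaches 4 months.

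Items 1 to 3 cost a few sentences in the SAP and use data already collected. Item 4 needs a short protocol clarification. The downside is that the sensitivity figure may be lower than the primary result, and item 2 counts as failures some leavers who may have done well.
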